7.2 Secondary Efficacy Endpoints

Secondary efficacy outcomes are proportional change in D-dimer level from baseline to 24 hours post-dose (Day 2) and Day 3, probability of discharge accompanied by ACTT ≥ 6 by Day 8 and Day 30, the secondary efficacy clinical composite, and change in biomarkers associated with outcomes including those related to coagulation and inflammation from baseline to Day 8 (or Day of Discharge if prior to Day 8). Inflammatory biomarkers include interleukin-6 (IL-6) and high sensitivity C-reactive protein (hsCRP), while coagulation biomarkers include prothrombin time (PT), partial thromboplastin time (PTT), factor Xa, and tissue factor.

7.2.1 Analysis of Secondary Efficacy Endpoints

Secondary efficacy endpoints will be subject to the same analysis, same sensitivity analyses, and same subgroup analyses as the primary efficacy endpoints.

7.2.2 Time to Recovery

Time to recovery by Day 30, with Day 1 being the date of randomization. Recovery is defined as the first day a participant meets criteria for category 6, 7, or 8 of the ACTT ordinal scale. The analysis of time to recovery will be a comparison of the combined rNAPc2 dose groups vs. SoC heparin by a stratified log-rank test, where stratification is according to local laboratory screening D-dimer level \leq or $> 2 \times$ local laboratory ULN. Cumulative incidence by treatment group will be summarized by Kaplan-Meier estimates. Additionally, a treatment hazard ratio and corresponding 95% confidence interval will be estimated by a Cox proportional hazard model stratified by local laboratory D-dimer level at screening. In addition, the two rNAPc2 dose groups will be compared for time to recovery.

Participants who die within 30 days of randomization will be censored at the day $x+1$, where x denotes the longest observation window among all subjects in the analysis. In addition, participants surviving to their Day 30 visit who have not met the criteria for recovery by the time of their last ACTT scale assessment on or prior to the Day 30 visit will be censored on the day of their last assessment on or prior to the Day 30 visit. There will be no censoring prior to Day 30 due to study treatment discontinuation,

initiation of non-study treatment, or intermittently missed ACTT scale assessments. Patients lost to follow-up or otherwise of unknown status occurring prior to Day 30 will be censored based on, and at the day of, the last known status.

The frequency and percentage of participants with each recovery category (ACTT equal to 6, 7, or 8) will be summarized.

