 - The need for inpatient medical services should be assessed daily after randomization until the participant is discharged from the hospital, deceased, or Day 30 visit is reached.
 - Documentation pertaining to this assessment must be provided to the CEC as outlined in the Site Manual.
- Clinical events and adverse events assessment
 - Assess for the occurrence of any adverse events and report via the eCRF as appropriate. See [Section 8.4 Adverse Events and Serious Adverse Events](#) for more information about adverse events.
 - Assess for the occurrence of any clinical event that suggests the possibility that an efficacy outcome event has occurred. See [Section 8.2 Efficacy Assessments](#) for more information about clinical events of interest.
- Post-COVID functional status (PCFS) scale
 - PCFS scale may be performed remotely e.g. by telephone.
 - For patients discharged on Day 30, a retrospective assessment of PCFS pre-COVID-19, which reflects functional status during the month preceding COVID-19 infection, should be performed after current PCFS assessment.
 - PCFS scale assessments should be omitted if the patient remains hospitalized through Day 30 as the instrument is intended to assess outpatient recovery.
- Vital Status (alive or deceased)
- Healthcare Resource Utilization Assessment
- Central laboratory samples (Phase 2b only)

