- Biomarkers associated with outcomes including those related to coagulation and inflammation (e.g., D-dimer, PT, PTT, Tissue Factor, factor Xa, antiphospholipid antibodies, IL-6, hsCRP).

ACTT ordinal scale: Study-site personnel will record ACTT information on the eCRF. Additionally, source documentation will be reviewed by the CEC which will adjudicate the ACTT and record the results in the

adjudication eCRF. The CEC will leverage the committee structure and collective experience to align on consistent criteria to distinguish between scores 5 and 6.

1. Death
2. Hospitalized, on invasive mechanical ventilation or extracorporeal membrane oxygenation
3. Hospitalized, on non-invasive ventilation or high flow oxygen devices
4. Hospitalized, requiring supplemental oxygen
5. Hospitalized, not requiring supplemental oxygen - requiring ongoing medical care (COVID-19 related or otherwise)
6. Hospitalized, not requiring supplemental oxygen - no longer requires ongoing medical care
7. Not hospitalized, limitation on activities and/or requiring home oxygen
8. Not hospitalized, no limitations on activities

Post-COVID-19 Functional Status Scale: The PCFS³¹ will be used to evaluate patient-reported functional status at hospital discharge, and 30-days post-randomization (if the patient has been discharged) (Figure 7). Retrospective assessment of pre-COVID-19 functional status will also be recorded. Instructions for using the scale are provided in Section 10.4.

[figure not shown]

Figure 7. Post-COVID Functional Status Scale

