9.4.2 ANALYSIS OF THE PRIMARY EFFICACY ENDPOINT(S)

Phase 2b: Primary efficacy endpoint is change in D-dimer level from Baseline to Day 8, or day of discharge if prior to Day 8. The change in D-dimer will be calculated using proportional change in D-dimer level from the level at baseline to the level at either Day 8 or discharge if discharge occurs before Day 8. A Wilcoxon rank sum test will be performed to compare baseline and Day 8 (or early discharge) D-dimer levels within each treatment group. A second Wilcoxon rank sum test will be used to compare proportional change from baseline to Day 8 (or early discharge) between treatment groups. The primary analysis will involve a comparison of the pooled rNAPc2 treatment groups against the heparin treatment group. Secondary and sensitivity analyses of the primary endpoint will be conducted as described in the statistical analysis plan.

Because the optimal dose rNAPc2 is unknown and its determination is a key objective of the Phase 2b study, the assumption that both doses will be effective and thus can be pooled for statistical analysis may not be correct. Therefore, a series of secondary analyses will be conducted, consisting of analysis for dose response, effectiveness in a single dose group, effectiveness that is related to the extent of baseline D-dimer elevation, and the subgroup analyses described in [Section 9.4.7 SubGroup Analyses](#).

Missingness within the data is to be expected. Subject profile, mortality, or early discharge give rise to the possibility that nonrandom attrition may bias the point estimate for the treatment effect for the primary endpoint. Therefore, missingness will be handled by multiple imputation during a sensitivity analysis as described in the Statistical Analysis Plan (SAP).

Phase 3: The primary efficacy endpoint is time to recovery by Day 30, with day 1 being the date of randomization. Recovery is defined as the first day a participant meets criteria for category 6, 7 or 8 of the ACTT ordinal scale. The analysis of the primary efficacy endpoint will be a comparison of the two treatment groups by a stratified log-rank test, where stratification is according to local laboratory screening D-dimer level $>$ or $\leq 2X$ local laboratory ULN. Cumulative incidence by treatment group will be

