summarized by Kaplan-Meier estimates. Additionally, a treatment hazard ratio and corresponding 95% confidence interval will be estimated by a Cox proportional hazard model stratified by local laboratory D-dimer level at screening.

In the analysis of the primary efficacy endpoint, participants who die within 30 days of randomization will be censored at Day 30. In addition, participants surviving to Day 30 who have not met the criteria for recovery by the time of their last ACTT scale assessment on or prior to Day 30 will be censored on the day of their last assessment. There will be no censoring prior to Day 30 due to study treatment discontinuation, initiation of non-study treatment, or intermittently missed ACTT scale assessments.

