3.0	
 • Corrected the censoring date for death in Section 7.2.2 to "day x+1, where x denotes the longest observation window among all subjects in the analysis" from “day of death”. This brings censoring date for death into alignment with the NAPc-201 clinical protocol language. • Added clarifying language to Section 7.2.3 regarding pre-existing organ support of any modality as an additional covariate, representing a special case arising from the specifications of the analysis.

List of Abbreviations

Abbreviation	Term
ACTT	Adaptive COVID-19 Treatment Trial
AE	Adverse Event
ATC	Anatomical Therapeutic Chemical
BMI	Body Mass Index
CEC	Clinical Endpoint Committee
CFR	Code of Federal Regulations
CI	Confidence Interval
CRF	Case Report Form
CSR	Clinical Study Report
CTMS	Clinical Trial Management System
DAPT	Dual Antiplatelet Therapy
DMP	Data Management Plan
DSMC	Data Safety Monitoring Committee
eGFR	Estimated Glomerular Filtration Rate
FDA	Food and Drug Administration
hsCRP	High Sensitivity C-reactive Protein
ICF	Informed Consent Form
IL-6	Interleukin-6
ITT	Intent-to-Treat
kg	Kilogram
LLN	Lower Limit of Normal
LMWH	low molecular weight heparin
MCAR	Missing Completely At Random
MedDRA	Medical Dictionary for Regulatory Activities
mg/dl	Milligram per deciliter
mITT	Modified Intent-to-Treat
mmHg	Millimeters of mercury

Abbreviation	Term
NSAIDS	Non-Steroidal Anti-Inflammatory Drugs
PCFS	Post-COVID Functional Status
PCR	Polymerase Chain Reaction
PT	Prothrombin Time
PTm	Preferred Term
PTT	Partial Thromboplastin Time
SAE	Serious Adverse Event
SAP	Statistical Analysis Plan
SC	Subcutaneous
SD	Standard Deviation
SoC	Standard of Care
SOP	Standard Operating Procedure
TEAE	Treatment-Emergent Adverse Event
TFLs	Tables, Figures, and Listings
UFH	Unfractionated Heparin
ULN	Upper Limit of Normal
URC	Unblinded Review Committee
WHO DDE	World Health Organization Drug Dictionary (Enhanced)

1 Introduction

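### The death-censoring rule for time to recovery covers every death by Day 30, so read literally it erases a recovery already observed; one limiting clause would bring it into line with the event definition

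*SAP*

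**What the plan says.** The event definition is the same in both documents. SAP 7.2.2: "Recovery is defined as the first day a participant meets criteria for category 6, 7, or 8 of the ACTT ordinal scale". Protocol 9.4.2 matches it apart from a comma. Neither requires the recovery to be sustained or the participant to be alive at Day 30.

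The death rule follows. SAP 7.2.2: "Participants who die within 30 days of randomization will be censored at the day" x+1, with x the longest observation window among the participants analysed. Protocol 9.4.2: "participants who die within 30 days of randomization will be censored at Day 30". Neither sentence mentions whether the participant had already recovered.

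The next sentence in each document deals with survivors, and it does carry that limit. In the SAP it applies to those "who have not met the criteria for recovery by the time of their last ACTT scale assessment on or prior to the Day 30 visit".

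The SAP revision history shows that version 3.0 revisited the death rule: "Corrected the censoring date for death in Section 7.2.2 to" the x+1 day. The entry concerns the date only. No order of precedence between the event definition and the death rule appears in either document.

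**The concern.** Placing deaths at or beyond the end of follow-up has a clear purpose: a participant who dies unrecovered stays in the risk set throughout and counts as never recovering. That works for deaths without recovery. As worded, however, the rule also takes in participants who recovered first and died later, and for them it contradicts the event definition.

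Such participants can occur and would be seen. Category 6 is reached in hospital ("Hospitalized, not requiring supplemental oxygen - no longer requires ongoing medical care"), categories 7 and 8 follow discharge, and the Day 30 visit records vital status for discharged participants too (Protocol 8.1.3).

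A program that applies the death sentence as written would turn observed recoveries into non-recoveries. A program that applies the first-day definition would keep them. The two would give different event counts and hazard ratios from the same data, in the Phase 3 primary endpoint (Protocol 9.4.2) and in the Phase 2b analysis, for which Protocol 9.4.3 adopts the Phase 3 methods.

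**Working it through.** **1. One patient under each sentence.** Category 6 on Day 7, discharged on Day 8, dies on Day 25.

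| Rule | Time | Status |
|---|---|---|
| First-day definition (both documents) | Day 7 | recovered |
| Death rule, SAP 7.2.2 | x+1 (Day 31 if x = 30) | censored, never recovered |
| Death rule, Protocol 9.4.2 | Day 30 | censored, never recovered |

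The conflict lies in the text and depends on no numerical assumption.

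**2. Phase 3 design figures, as the base for an illustration.** Protocol 9.2 gives 450 participants 1:1, 360 events, medians of 11 and 15 days (HR 1.36) and approximately 80% power at two-sided 5%. With exponential recovery times, the probability of recovery by Day 30 is 1 − 2^(−30/median):

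- rNAPc2: 1 − 2^(−30/11) = 0.849, and 225 × 0.849 = 191.0
- heparin: 1 − 2^(−30/15) = 0.750, and 225 × 0.750 = 168.8
- total: 359.8, which reproduces 360.

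Schoenfeld power is Φ(√360 × ln 1.36 / 2 − 1.96) = Φ(0.957) = 83.1%; the Freedman formula gives 82.5%. The stated power is therefore slightly conservative, which has no bearing on this point.

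**3. Size at the Phase 3 design.** The documents give no rate of death after recovery, so the shares below are assumptions. There were 3,000 simulated trials per row, with 225 per arm, daily recovery times and an unstratified log-rank test at two-sided 0.05. Recovered patients who later die are coded either as events on the recovery day or as censored after Day 30.

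| Assumed share of recovered who die by Day 30 (rNAPc2 / heparin) | Power, first-day rule | Power, literal death rule | Trials where the significance verdict differs |
|---|---|---|---|
| 1% / 1% | 83% | 82% | 4% |
| 2% / 2% | 83% | 80% | 6% |
| 5% / 5% | 84% | 77% | 11% |
| 3% / 2% | 83% | 73% | 11% |
| 5% / 2% | 84% | 59% | 25% |
| 2% / 5% | 84% | 92% | 8% |

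At 2% in both arms, 0.02 × 360 ≈ 7 events are affected. A separate run of 1,500 trials gave 84% against 80% for that row. A run of 2,500 trials at 0.5% in both arms gave 82.8% against 82.6%, with verdicts differing in 2%.

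**4. Size at the Phase 2b design.** 160 participants randomized 1:1:2 give 80 pooled rNAPc2 against 80 heparin. The Phase 3 medians are borrowed, since no Phase 2b recovery times are stated. Expected events are 80 × 0.849 + 80 × 0.750 = 127.9. Means over 400 simulated trials, with HR above 1 favouring rNAPc2:

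| Assumed share (rNAPc2 / heparin) | Events, first-day vs literal | HR, first-day vs literal |
|---|---|---|
| 2% / 2% | 128.0 vs 125.4 | 1.42 vs 1.41 |
| 5% / 5% | 128.6 vs 122.3 | 1.40 vs 1.36 |
| 5% / 2% | 128.0 vs 123.6 | 1.41 vs 1.30 |
| 2% / 5% | 127.5 vs 123.1 | 1.44 vs 1.50 |

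At 0.5–2% in both arms, about 1 to 3 patients are affected (0.005 × 128 = 0.6; 0.02 × 128 = 2.6).

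**The case against.** The strongest answer is convention: censoring applies to participants without an event, so a recovery on Day 7 stands whatever happens on Day 25. The documents lend this some support. The lost-to-follow-up sentence in SAP 7.2.2 also lacks a limit to the unrecovered, and nobody would read it as cancelling a recovery seen before contact was lost. For the mortality and thrombosis endpoints, SAP 7.3.1 and Protocol 9.4.3 censor only participants without an adjudicated event. The survivor sentence needs its qualifier because most survivors recover, so the contrast in wording proves less than it first suggests.

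Most of this stands, and convention is probably what was meant. It does not close the gap, because the death rule is not ordinary censoring. It overrides the actual date of death so that death counts as never recovering, and a programmer following that logic could reasonably apply it to every death.

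The setting also limits the point. SAP 7.2.2 governs Phase 2b only, where time to recovery is not primary and no power is claimed for it. SAP section 1 defers Phase 3 reporting to a separate plan, which under Protocol 9.4.1 would supersede the protocol text on analysis. Protocol 9.4.2 is nonetheless the current statement of the Phase 3 primary analysis, and a Phase 3 plan could inherit its wording.

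A reader might infer that the coding would be chosen once deaths by arm are known. The documents do not support that: SAP 3.3 has programs developed before database lock run on dummy treatment codes, and SAP section 4 requires an approved amendment for major changes.

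**Conclusion.** The death rule is broader than the event definition allows. Read literally, it recodes an observed recovery as a non-recovery, and neither document states which rule prevails. This is a wording error with a probable intended meaning, not a flaw in the choice of endpoint or in handling unrecovered deaths as never recovering.

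Its size depends wholly on assumed rates of death after recovery. With 1–2% in both arms, power at the Phase 3 design differs by about 1 to 4 points. In Phase 2b, 2% in both arms moves the mean hazard ratio from 1.42 to 1.41. The effect becomes appreciable when such deaths differ by arm, and its direction follows the arm with more of them.

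A reader might take the fall from 84% to 59% as the likely cost. It requires an assumed 5% against 2%, a 2.5-fold excess on rNAPc2, which nothing in the documents suggests and which the mortality and composite analyses would also reflect. The figures illustrate direction and order of magnitude only.

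The point is modest for Phase 2b and matters more for the Phase 3 primary endpoint.

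**What to change.** In SAP 7.2.2 and Protocol 9.4.2, limit the death sentence by inserting *without having met the recovery criteria* after the words on dying within 30 days of randomization. Leave the rest of each sentence as it is. An observed first recovery then stands as an event, and deaths without recovery are handled as now. Carry the same wording into the Phase 3 analysis plan.

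The cost is one clause in each document, with no new data and no change to the sample size.

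A sensitivity analysis in which death or rehospitalization by Day 30 cancels a recovery is optional and not part of this correction. It addresses a different question, that of sustained recovery. Because daily ACTT scoring stops at discharge (Protocol 8.1.1), a later relapse could not be scored directly and would have to be inferred from rehospitalization and vital status.

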7.2.3 Composite of Clinical Events

The secondary efficacy clinical composite will be measured and compared between treatment groups. This composite will consist of death (all-cause), thrombotic events (Stroke, MI, PE, peripheral arterial and clinically relevant deep vein thrombosis), organ support as defined in [Section 7.3.2](#), and rehospitalizations adjudicated as to its relatedness to COVID-19.

The primary formulation of the composite will limit the number of contributing events per component per patient to one, i.e., the aggregate will have values from 0 – 4 for each patient. The component-wise analysis will be performed using logistic regression, where the contribution of each component is necessarily a dichotomous variable. The aggregate will be analyzed using Poisson regression.

The secondary formulation will differ from the primary in that no limitation on the component-wise contributions will be imposed. Thus, component-wise analysis will also be Poisson regression except in the case of death or any data-driven circumstance where the only available values are binary.

Regression models will include treatment in the unadjusted formulation, and treatment, D-dimer stratum and pre-specified subgroups in the covariate-adjusted formulation. Pre-existing organ support of any modality is discussed below as an additional covariate, representing a special case arising from the specifications of the analysis.

Assumptions inherent to any of these models, e.g., whether data manifest in accordance with a Poisson distribution (where λ , the rate, is both mean and variance) will be tested. In the case of Poisson, testing significant deviations from assumptions will use Likelihood Ratio tests on Zero-inflated and/or Negative Binomial operationalizations of the dependent variable distribution (these are not mutually exclusive). Both Logistic and Poisson regression models may remove variables that introduce issues in the model estimation process, e.g., a regressor with no variance, cell sparsity, or sufficient multicollinearity to induce rank deficiency of the model-implied design matrix will flatten the likelihood function, destabilizing point estimates and inflating confidence intervals by orders of magnitude.

Events in these analyses must be treatment-emergent to be eligible for inclusion, and therefore subjects with pre-existing organ support will need adjustment in order to properly estimate effects related to initiation of new organ support. This will manifest as a binary covariate indicating pre-existing organ support of any modality.

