2.5 Secondary Endpoints

2.5.1 Efficacy

Secondary efficacy endpoints are:

- Change in D-dimer level from baseline to 24 hrs post the institution of study medication following randomization (Study Day 2), and 48 hours after institution of study medication (Study Day 3)
- Probability of discharge as assessed by ACTT ≥ 6 by Day 8 and Day 30 post randomization
- Composite of death, thrombosis, organ support, or rehospitalization within 30 days adjudicated as to its relatedness to COVID-19
- Change in biomarkers associated with outcomes including those related to coagulation and inflammation from baseline through Day 8

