7.3.2 Healthcare Resource Utilization

Days in intensive care unit, on ventilator, vasopressors, renal replacement therapy, and circulatory support will be summarized with descriptive statistics.

Organ support free days will be compared between the rNAPc2 and heparin arms via Wilcoxon Rank Sum testing, as in analysis of the Primary Efficacy Endpoint. Organ support free days is defined as total number of days without any of the following: placement on invasive mechanical ventilation, intravenous inotrope or vasopressor administration, renal dialysis, mechanical circulatory support, or death will be documented for each patient, and the number of total as well as individual interventions per patient will be compared by treatment group. Subjects who die are assigned a score of -1 for organ support free days. In the event that a large number of ties exist (e.g., a substantial proportion of subjects have the entire 30 days free of organ support), then organ support free days will be categorized as 30, 0-29, and -1 representing no organ support needed, some organ support needed, and death, respectively. An equivalent scenario involving every day requiring organ support for many subjects would yield 1-30, 0, -1 as categories. This tabulation will be analyzed subsequently using an Exact Wilcoxon test, such that ordinality across categories is maintained. In a circumstance where only two of the three categories are observed, this becomes an exact binomial test.

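### The secondary clinical composite scores death as 1 on an unweighted 0–4 count, so a patient who dies with no other component scores better than a survivor with two

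*SAP*

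**What the plan says.** SAP 2.5.1 lists, as one of four secondary efficacy endpoints, a "Composite of death, thrombosis, organ support, or rehospitalization within 30 days".

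SAP 7.2.3 sets out the analysis. The components are all-cause death, thrombotic events, organ support (defined by reference to 7.3.2) and rehospitalization adjudicated for its relation to COVID-19.

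- **Primary formulation:** "The primary formulation of the composite will limit the number of contributing events per component per patient to one", so that "the aggregate will have values from 0 – 4 for each patient". Then: "The aggregate will be analyzed using Poisson regression".
- **Secondary formulation:** "The secondary formulation will differ from the primary in that no limitation on the component-wise contributions will be imposed".
- **Model terms:** "Regression models will include treatment in the unadjusted formulation, and treatment, D-dimer stratum and pre-specified subgroups in the covariate-adjusted formulation". A covariate for pre-existing organ support is added. No weight for death, no hierarchy and no time-at-risk offset is stated.

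For organ-support-free days, SAP 7.3.2 handles death differently: "Subjects who die are assigned a score of -1 for organ support free days".

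**The concern.** A summed score implies a severity order: a higher total is worse. Under 7.2.3 that order fails at the point that matters most. Death carries the same weight as one rehospitalization, and a patient who dies early can collect no further points. A treatment that turned complicated survival into early death would lower the mean count and look beneficial.

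The secondary formulation widens the gap. A survivor with one thrombosis and three rehospitalizations scores 2 when capped and 4 when uncapped, while a death still adds one point.

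The SAP avoids this ordering for organ-support-free days, which is exploratory, but not for the composite, which is secondary.

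**Working it through.** **Inputs from the documents.** Four components, each capped at 1 (SAP 7.2.3). 160 participants randomized 1:1:2 (SAP 2.2), so pooled rNAPc2 is 40 + 40 = 80 and heparin is 80. Two-sided alpha of 0.05 (SAP 7.4). The documents give no event rates for the components, so all counts below are assumptions.

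**Step 1: the plan's range.** The sum of four 0/1 items takes the values 0, 1, 2, 3 and 4, which matches the SAP.

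**Step 2: patient-level order.** There are 8 fatal and 8 survivor profiles, so 64 pairs. A fatal profile with j non-fatal components scores 1 + j; a survivor with k scores k. The number of profiles with 0, 1, 2 or 3 non-fatal components is 1, 3, 3, 1.
- Fatal scores better (1 + j < k): (j=0, k=2) 3, (j=0, k=3) 1, (j=1, k=3) 3; total 7.
- Tie (k = 1 + j): 3 + 9 + 3 = 15.
- Fatal scores worse: 64 − 7 − 15 = 42.

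**Step 3: illustration A (assumed).**
- Heparin: 8 deaths only, 8 survivors with two components, 16 with one, 48 with none. Total = 8×1 + 8×2 + 16×1 = 40; mean 0.50.
- rNAPc2: the 8 two-component survivors instead die early. Total = 16×1 + 16×1 = 32; mean 0.40.
- Rate ratio = 32/40 = 0.80. SE of the log ratio = √(1/32 + 1/40) = 0.237; z = ln(0.80)/0.237 = −0.94; p = 0.35.
- Mortality is 16/80 = 20% against 8/80 = 10%. The count favours the arm with double mortality, but not significantly.

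**Step 4: illustration B (assumed).** 13 deaths only, against 4 deaths only plus 12 survivors with two components.
- Totals 13 and 4 + 24 = 28; rate ratio 0.46. SE = √(1/13 + 1/28) = 0.336; z = −2.29; p = 0.022 (sandwich p = 0.026).
- Fisher's exact test on death gives p = 0.038 in the opposite direction.

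**Step 5: death ranked worst.**
- A, death set to 4: heparin (8×4 + 8×2 + 16)/80 = 0.80; rNAPc2 (16×4 + 16)/80 = 1.00. The order reverses. The probability that a random rNAPc2 patient fares better, ties counted half, moves from (48×56 + 32×20)/6400 = 0.52 on the count to (48×56 + 16×24 + 16×4)/6400 = 0.49.
- B: Wilcoxon with death worst gives p = 0.83 and a probability of 0.507. The significant win disappears, though the estimate still leans slightly to the arm with more deaths.

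**Step 6: any component, yes or no.** Illustration A gives 8 + 8 + 16 = 32/80 against 16 + 16 = 32/80. The false advantage goes, but the doubled mortality is invisible.

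**Step 7: how often.** In simulations with assumed mortality of 10% against 5%, the higher-mortality arm won significantly on the Poisson count in:
- 0.2–0.6% of runs with equal non-fatal rates (thrombosis 8%, organ support 12%, rehospitalization 6%);
- 16–26% of runs with its non-fatal rates about halved (5/8/4% against 10/18/8%). Death-worst ranking gave 22–24% in that same scenario.

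**The case against.** **A reversal would not be hidden.** SAP 7.2.3 and Section 10 require component-wise analysis, which includes death. SAP 7.3.1 plans time to all-cause mortality, and 7.3.2 scores death worst for organ-support-free days. This stands as mitigation. However, the aggregate is analysed first, and no conclusion from it depends on mortality.

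**Death need not score 1.** A death after organ support scores 2 and ties with a two-component survivor. In addition, the organ-support definition in 7.3.2 closes its list with death. Read literally, every death scores 2: illustration A becomes 16×2 + 16 = 48 against 8×2 + 8×2 + 16 = 48, and B becomes 26 against 32 (ratio 0.81). That weakens the examples, but death would still beat a three-component survivor, and the SAP should not leave the reading open.

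**The test is unclear.** SAP 7.2.1 gives secondary endpoints the primary endpoint's analysis (Wilcoxon), while 7.2.3 says Poisson. A Wilcoxon test on the raw count in B gives p = 0.31. The patient-level order is the same under either test.

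**Stronger readings that the documents do not support.**
- *The arm with more deaths should be expected to win.* No component rates are given, and with equal non-fatal rates it won in under 1% of simulated trials.
- *The planned test has badly inflated type I error.* With assumed rates of 10, 15, 5 and 5% and 80 per arm, plain Poisson gave 3.5%, 6.5% and 12.8% at latent correlation 0, 0.3 and 0.6. But 7.2.3 plans likelihood ratio checks against negative binomial and zero-inflated models. Switching to negative binomial when the check was significant gave 3.5%, 5.5% and 5.0%; the switching rule is an assumption, since the SAP states none.
- *This is the leading clinical secondary endpoint.* SAP 2.5.1 lists four secondary endpoints without rank.
- *Reverting to the either/or wording of 2.5.1 cures the problem.* Step 6 shows that it does not.

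**Conclusion.** The point holds as a scoring defect. As written, the count ranks a death-only patient above a survivor with two components, and lifting the cap widens the gap. An arm with more deaths can score better: by 20% without significance in illustration A, and by 54% with p=0.022 in illustration B. Both results rest on assumed counts and on deaths that carry no other component. The companion analyses would expose such a result but would not change the aggregate's direction. The primary D-dimer analysis is not affected. The SAP should be changed before the composite is interpreted.

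**What to change.** In SAP 7.2.3:

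1. In the primary formulation, assign the worst score (4) to any death within 30 days, consistent with the rule in 7.3.2 for organ-support-free days.
2. Compare arms by a Wilcoxon rank sum test stratified by D-dimer stratum. This also brings 7.2.3 into line with the test family that 7.2.1 implies.
3. Report all-cause mortality beside the composite. Worst-ranking alone does not stop an arm with more deaths winning through fewer non-fatal events (step 7).
4. State that death is not itself organ support for this composite.
5. Report the any-event yes/no analysis, if wanted, as supportive only. If Poisson regression is kept, make it supportive with sandwich standard errors.

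**Cost.** SAP wording only; data collection and adjudication are unchanged. The treatment effect is no longer a rate ratio, and non-fatal events in patients who die no longer add to the score.
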